7.4.5. Change from baseline in median Spearman-Kärber estimates

• Computation of the Endpoint

Frequency Therapeutics

Protocol No. FX-322-208

Change from baseline to each post-baseline visit in median Spearman-Kärber estimates will be computed as dB post-baseline – dB at baseline. Missing data will not be imputed.

• Analysis of the Endpoint

The change from baseline in median Spearman-Kärber estimates will be summarized descriptively for treated ears by visit and treatment group for subjects in the FAS.

In treated ears only for subjects in the FAS, post-baseline treatment group comparisons through day 90 for the change from baseline in median Spearman-Kärber estimate will be analyzed using a MMRM model. The model will include fixed covariates of treatment group, visit, interaction between visit and treatment group, baseline median Spearman-Kärber estimate, interaction between baseline median Spearman-Kärber estimate and visit, and randomization stratification factors. If the model fails to converge, the randomization stratification factors will be dropped from the model. An unstructured covariance will be used to model the within-subject errors. Linear contrasts will be constructed to estimate the treatment effect on the mean change from baseline in median Spearsman-Kärber estimate by visit (e.g., estimated LS Mean differences by visit).

Line graphs (with standard error bars) will be created for the adjusted (least squares) mean change from baseline in median Spearman-Kärber estimates for treated ears by postbaseline visit and treatment group for subjects in the FAS. Post-baseline visit will be plotted on the x-axis and the adjusted (least squares) mean change from baseline in median Spearman-Kärber estimates for treated ears will be plotted on the y-axis. Each treatment group will be presented as a separate line in the plot.

7.4.6. Improvement ≥3 dB shifts in median Spearman-Kärber estimates from baseline

• Computation of the Endpoint

Improvement \geq 3 dB shifts in median Spearman-Kärber estimates at each post-baseline visit for treated ears will be computed as 1 if the post-baseline Spearman-Kärber estimate – baseline Spearman-Kärber estimate is \geq 3 and as 0, otherwise where the baseline and postbaseline Spearman-Kärber estimates are not missing. Missing data will not be imputed.

• Analysis of the Endpoint

The incidence of improvement ≥3 dB shifts in median Spearman-Kärber estimates at each post-baseline visit for treated ears will be summarized using frequencies and percentages by visit and treatment group for subjects in the FAS.

Post-baseline treatment group comparisons will be performed using the GEE model described in Section 7.4.3 for subjects in the FAS.

Version Date: 2	2023-01-19
-----------------	------------

7.5. Patient Global Impression of Severity/Patient Global Impression of Change

PGI-S Hearing Loss Scale, administered at the End of Lead-In/Treatment visit, is a patient reported outcome (PRO) measure for subjects to best describe the severity of their hearing loss over the past week.

PGI-C Hearing Loss Scale, administered at the Day 90 visit, is a PRO measure to describe the overall change in their hearing loss after study drug administration.

PGI-S Daily Impacts Scale, administered at the End of Lead-In/Treatment visit, is a PRO measure for subjects to best describe the impact of their hearing loss on daily activities.

PGI-C Daily Impacts Scale, administered at the Day 90 visit, is a PRO measure to describe the overall change in the impact of their hearing loss on daily activities since study drug administration.

7.5.1. PGI-S hearing loss scale responses

• Computation of the Endpoint

Categories will be assigned to numeric values as follows: "None" = 1, "Mild" = 2, "Moderate" = 3, "Severe" = 4, and "Very Severe" = 5.

• Analysis of the Endpoint

The number and of percentage of subjects in each category ("None", "Mild", "Moderate", "Severe", "Very Severe") in PGI-S hearing loss scale will be summarized descriptively by treatment group for subjects in the FAS. The numeric values will be used as a covariate for analyzing the PGI-C hearing loss scale.

7.5.2. PGI-C hearing loss scale responses

• Computation of the Endpoint

Categories will be assigned to numeric values as follows: "Much better" = 1, "A little better" = 2, "No change" = 3, "A little worse" = 4, and "Much worse" = 5.

• Analysis of the Endpoint

The number and of percentage of subjects in each category ("Much better", "A little better", "No change", "A little worse", "Much worse") in PGI-C hearing loss scale will be summarized descriptively by treatment group for subjects in the FAS.

Additionally, as a key secondary efficacy analysis, the average response in PGI-C hearing loss scale, using the assigned numeric values of 1-5, will be compared between treatment groups at Day 90. An ANCOVA model, adjusting for the subject's baseline PGI-S hearing loss

scale category as a quantitative covariate using the assigned numeric values of 1-5, will be used. Subjects with missing data at Day 90 will be excluded from analysis.

- 7.5.3. PGI-S daily impacts scale responses
 - Computation of the Endpoint

Categories will be assigned to numeric values as follows: "None" = 1, "Mild" = 2, "Moderate" = 3, "Severe" = 4, and "Very Severe" = 5.

• Analysis of the Endpoint

The number and of percentage of subjects in each category ("None", "Mild", "Moderate", "Severe", "Very Severe") in PGI-S daily impacts scale will be summarized descriptively by treatment group for subjects in the FAS. The numeric values will be used as a covariate for analyzing PGI-C daily impacts scale.

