2.3. Randomization

Subjects will be randomized in a 1:1 ratio to one of two groups (FX-322 or placebo, respectively). The randomization will be stratified for Visit 2 (Day -15) Maryland CNC Word Recognition Score (above or equal to 28% words in quiet correct and below 28% words in quiet correct) and unilateral versus bilateral hearing loss. A single injection of FX-322 or placebo will be administered on Day 1 by intratympanic injection in the study ear.

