4. ANALYSIS SETS

Analysis sets in this study are defined in the following:

• Full Analysis Set

The Full Analysis Set (FAS) includes all randomized subjects who receive one dose of study drug (regardless of whether a full dose was administered) in the study ear. Subjects will be analyzed according to their randomized treatment group.

• Per Protocol Analysis Set

The Per Protocol Analysis Set (PPAS) includes subjects in the FAS receiving one full dose of study drug in the study ear to be treated per the randomization treatment schedule and without major protocol deviations as defined in Section 6.1. PPAS subjects will be analyzed according to their randomized treatment group.

• Safety Analysis Set

The Safety Analysis Set (SfAS) includes all subjects who receive one dose of study drug (regardless of whether a full dose was administered) in any ear and will be analyzed according to the actual treatment received. For safety assessments completed by ear for each subject, results from actual treated and actual untreated ears will be summarized separately. The SfAS will be used for the analysis of safety.

All main efficacy analyses will be based on FAS, with sensitivity analyses for primary and key secondary endpoint analyses in the PPAS. If more than 10% of subjects in the FAS are excluded from the PPAS, additional sensitivity analyses, other than for the primary and key secondary endpoints based on PPAS, may be performed.

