7.1.4. Multiplicity Adjustment

A fixed-sequence testing procedure will be implemented to control the family-wise type I error rate at 5% for the primary and key secondary endpoints as presented graphically in Figure 1. The hypothesis of superiority on the primary and key secondary efficacy endpoints of FX-322 versus placebo will be tested in the hierarchical order. The primary efficacy endpoint, incidence of subjects who have a Word Recognition in Quiet (Maryland CNC) improvement at Day 90, will be tested first, using the primary analysis approach described in Section 7.3.1. If superiority of FX-322 over placebo in improving speech perception for Word recognition in Quiet (WR) is established, the treatment effect in the key secondary endpoint, WIN improvement based on mean change from baseline in percentage of recognized words overall at Day 90, will be tested subsequently, using the analysis approach described in Section 7.4.2. If superiority of FX-322 over placebo is established for the key secondary endpoint, the treatment effect the next key secondary efficacy endpoint, Patient Global Impression of Change (PGI-C) Hearing Loss Scale responses at Day 90, will be tested subsequently, using the analysis approach described in Section 7.5.2. Lastly, if superiority of FX-322 over placebo is established for the previous three endpoints, the treatment effect for PGI-C Daily Impacts Scale responses at Day 90 will be tested subsequently, using the analysis approach described in Section 7.5.4.

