Percentage of recognized words	Descriptive summary for treated and untreated ears	7.4.1
Change from baseline in percentage of recognized	Descriptive summary for treated and untreated ears	7.4.2

Version Date: 2023-01-19

Page 20 of 64

Endpoint	Analysis Method(s)	Section
words (Key Secondary Efficacy Endpoint)	• Line graphs (with standard error bars) for adjusted least squared means in change from baseline for treated ears	
	Primary Analysis: MMRM in treated ears	
	• Sensitivity Analysis: MMRM in treated ears for PPAS	
Improvement ≥10% (7 words) from baseline in percentage of recognized words	Descriptive summary for treated earsGEE in treated ears	
Spearman-Kärber estimates of decibel (dB) thresholds for word recognition (25 th , 50 th (median) and 75 th percentiles)	 Descriptive summary for treated ears Scatter plots for treated ears 	7.4.4
Change from baseline in median Spearman-Kärber estimates	 Descriptive summary for treated ears Line graphs (with standard error bars) for adjusted least squared means in change from baseline for treated ears MMRM in treated ears 	
Improvement ≥3 dB shifts in median Spearman-Kärber estimates from baseline	Descriptive summary for treated earsGEE in treated ears	7.4.6
Patient Global Impression of	Severity and Patient Global Impression of Change*	7.5
PGI-S hearing loss scale responses	Descriptive summary for treated ears	7.5.1
PGI-C hearing loss scale responses (Key Secondary Efficacy Endpoint)	Analysis of Covariance (ANCOVA) in treated ears	7.5.2
PGI-S daily impacts scale responses	Descriptive summary for treated ears	7.5.3
PGI-C daily impacts scale responses (Key Secondary Efficacy Endpoint)	ANCOVA in treated ears	7.5.4
Pure Tone Audiometry		7.6
Air Conduction (AC) and Bone Conduction (BC) audiometry dB hearing level (HL) thresholds by frequency	Descriptive summary for treated and untreated ears	7.6.1

Endpoint	Analysis Method(s)	Section
Mean overall pure tone average (PTA) (AC over 0.5, 1, 2, and 4 kHz) and Bone Conduction Average (BCA) (BC over 0.5, 1, 2 and 4 kHz)	Descriptive summary for treated ears	7.6.2
AC and BC improvement ≥10 and ≥15 dB HL from baseline, separately, for two contiguous frequencies	Descriptive summary for treated ears	7.6.3
AC and BC improvement ≥15 and ≥20 dB HL from baseline, separately, for any frequency	Descriptive summary for treated ears	7.6.4
AC and BC composite improvement from baseline	Descriptive summary for treated earsGEE in treated ears	7.6.5

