7.2.3. Other Key Secondary Efficacy Endpoints

Variables: PGI-C hearing loss scale response and PGI-C daily impacts scale response at Day 90.

Population: The analysis population will be the FAS.

Intercurrent events: Subjects who do not have these assessments completed at Day 90 will be assumed missing at random, and no responses will be imputed.

Population-level summary: Comparison of mean difference between treatment groups at the Day 90 visit.

Additional details on the computation, analysis, and sensitivity analyses for these secondary efficacy endpoints can be found in Section 7.5.2 and 7.5.4.

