The primary efficacy analysis will be conducted for the incidence of WR improvement at Day 90 in treated ears for subjects in the FAS using a 1 degree of freedom Chi-Square test for a single 2x2 table without stratification. Although the randomization was stratified by Visit 2 WR Maryland CNC score (>= 28% vs < 28%) and laterality of hearing loss (bilateral vs unilateral), the randomization was done to maintain balance among the treatment groups across the randomization factors to help interpretation of the results rather than any prognostic status. As such, it is believed the unstratified primary analysis will be more straightforward in interpretation, especially if some of the sample sizes in individual strata are small.

• Sensitivity Analyses of the Endpoint

The Chi-Square test will be repeated using treated ears for subjects in the PPAS. Additionally, the Chi-Square test will be performed with improvement being defined as an increase in post-baseline WR score above the 90%, 85%, and 80% upper limit based on baseline assessment using Carney-Schlauch method for treated ears. The 90%, 85%, and 80% upper limits will be determined based on simulation using the same approach used to compute the 95% limits described by Carney-Schlauch (2007).

A two-sided 95% CI for the odds ratio for the incidence of improvement between the treatment groups for treated ears will also be computed using the Cochran-Mantel-Haenszel (CMH) chi-square test, adjusted for the randomization stratification factors.

A GEE model will be utilized to estimate an odds ratio and its associated 95% CI between the treatment groups at each visit for treated ears. With the binomial distribution assumption and logit link, the model will include fixed effects of treatment group, visit, interaction between visit and treatment group, baseline WR score, interaction between baseline WR score and visit, and randomization stratification factors. The model will utilize an unstructured working correlation matrix. If the model fails to converge, the randomization stratification factors will be excluded from the model. The odds ratios along with 95% CIs and p-values between treatment groups will be reported by visit.

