7.5.4. PGI-C daily impacts scale responses

• Computation of the Endpoint

Categories will be assigned to numeric values as follows: "Much better" = 1, "A little better" = 2, "No change" = 3, "A little worse" = 4, and "Much worse" = 5.

• Analysis of the Endpoint

The number and of percentage of subjects in each category ("Much better", "A little better", "No change", "A little worse", "Much worse") in PGI-C daily impacts will be summarized descriptively by treatment group for subjects in the FAS.

Additionally, as a key secondary efficacy analysis, the average response in PGI-C daily impacts scale, using the assigned numeric values of 1-5, will be compared between treatment groups at Day 90. An ANCOVA model, adjusting for the subject's baseline PGI-S daily impacts scale category as a quantitative covariate using the assigned numeric values of 1-5, will be used. Subjects with missing data at Day 90 will be excluded from analysis.

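### The two PGI-C key secondary ANCOVAs leave out the randomization factors, and PGI-C alone among the confirmatory endpoints has no stratum-adjusted result planned (low priority, near-free improvement)

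*SAP*

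**What the plan says.** SAP 2.3 stratifies randomization by Visit 2 Maryland CNC score (28% or above against below 28%) "and unilateral versus bilateral hearing loss".

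SAP 7.1.4 tests four endpoints in fixed sequence at a family-wise 5%: WR, WIN, PGI-C Hearing Loss, PGI-C Daily Impacts. The last is tested only "if superiority of FX-322 over placebo is established for the previous three endpoints".

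The factors are handled differently along that sequence:

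- **WR (7.3.1):** the primary test is an unstratified chi-square. CMH, GEE and inverse-variance (DerSimonian-Laird) sensitivity analyses adjust for the factors.
- **WIN (7.4.2):** the confirmatory MMRM includes the factors and drops them only if it does not converge.
- **PGI-C Hearing Loss (7.5.2):** ANCOVA with baseline PGI-S, "scale category as a quantitative covariate using the assigned numeric values of 1-5, will be used". No factors.
- **PGI-C Daily Impacts (7.5.4):** ANCOVA with "baseline PGI-S daily impacts scale category as a quantitative covariate". No factors.

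On sensitivity analyses, 7.2.3 tells the reader that "sensitivity analyses for these secondary efficacy endpoints can be found in Section 7.5.2 and 7.5.4". Neither section contains one. Table 7-2 gives a single method for PGI-C Hearing Loss, "Analysis of Covariance (ANCOVA) in treated ears", and likewise only ANCOVA for Daily Impacts. Section 4, however, makes a general commitment: main efficacy analyses use the FAS, "with sensitivity analyses for primary and key secondary endpoint analyses in the PPAS".

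Protocol 15.5 calls for baseline and stratification-factor adjustment only where appropriate, and leaves the details to the SAP.

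**The concern.** When randomization is stratified and the strata predict the outcome, the arms are more alike than simple randomization would make them. A model that omits the strata does not credit that balance: its standard error is too large, its interval too wide and its test conservative.

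The omission also stands out within the SAP. The other regression models (WR GEE and arcsine MMRM; WIN MMRM and GEE; Spearman-Kärber MMRM and GEE; the audiometry GEEs) all start with the factors and drop them only on non-convergence. No reason is given for treating PGI-C differently. Laterality could plausibly matter here, because PGI-C rates the subject's hearing loss as a whole while one ear is injected, but the documents give no data on this.

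At stake is a little power on the third and fourth confirmatory tests. There is also a documentation gap: a programmer following 7.2.3 does not find the prespecified PGI-C sensitivity analyses where the SAP says they are.

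**Working it through.** **The plan's own figure.** 112 evaluable with 10% dropout: 112 / 0.9 = 124.4, against 124 stated (124 × 0.9 = 111.6). This agrees to within rounding. The 80% power is stated for WR only, and its responder rates are in the unmasked addendum, so it cannot be reproduced. No power is stated for PGI-C.

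**Inputs from the SAP.** N = 112, 1:1; two-sided 5%; the order of testing.

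**Assumed inputs, not in the documents.** Standardized PGI-C difference d = 0.534 (gives 80% power when the strata explain nothing); near-balanced strata; R², the share of PGI-C variance left after PGI-S that the two factors explain, at 0, 2, 5 and 10%.

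**Formulas (noncentral t).**

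- Residual df without the factors: 112 − 3 = 109 (intercept, treatment, PGI-S). With two more main effects: 107.
- Noncentrality under stratified randomization, either model: d/√(1−R²) × √112/2.
- Critical value with the factors: t(0.975, 107) = 1.982.
- Without them, the reported standard error is too large by 1/√(1−R²), so the effective critical value is t(0.975, 109)/√(1−R²).
- True size without the factors: 2 × P(t on 109 df > that value).

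Example, R² = 5%: 1/√0.95 = 1.026; noncentrality 0.534 × 1.026 × 5.292 = 2.90; effective critical value 1.982 × 1.026 = 2.033.

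| R² | True size without | Power without | Power with | Difference (points) |
|---|---|---|---|---|
| 0% | 5.0% | 80.0% | 80.0% | −0.01 |
| 2% | 4.8% | 80.2% | 80.7% | 0.54 |
| 5% | 4.4% | 80.6% | 81.9% | 1.37 |
| 10% | 3.9% | 81.2% | 83.9% | 2.73 |

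**Simulation check.** 20,000 runs per cell; score rounded to 1–5; PGI-S in both models; blocks of 4 within four unequal strata (35/30/20/15%); assumed effect 0.4 and SD 0.75. Power without against with: 73.4 and 73.2% (R² = 0), 73.7 and 75.2% (5%), 74.8 and 78.1% (10%). Null rejection: 5.2 and 5.3%, 4.4 and 4.7%, 4.0 and 4.8% (Monte Carlo standard error about 0.15 point). Direction and size agree.

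**After gatekeeping,** assuming 80% power for each earlier test:

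- PGI-C Hearing Loss is reached with probability 0.8 × 0.8 = 0.64 (independent tests) to 0.80 (fully dependent). R² = 5%: 1.37 × 0.64 to 1.37 × 0.80 = 0.9 to 1.1 points. R² = 10%: 2.73 × 0.64 to 2.73 × 0.80 = 1.7 to 2.2 points.
- PGI-C Daily Impacts, three independent gates each held at 80%: 0.8³ = 0.512, so 0.7 points (R² = 5%) and 1.4 points (R² = 10%). This credits only the Daily Impacts model. If both models are adjusted, the Hearing Loss gate is also passed more often: at R² = 5%, 0.64 × (0.8194² − 0.8057²) = 1.4 points in total; at R² = 10%, 0.64 × (0.8393² − 0.8120²) = 2.9 points.

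**The case against.** The strongest case against is that there is no statistical fault to correct. ANCOVA on PGI-S alone is a legitimate prespecified model, any error is conservative, and the protocol leaves the choice to the SAP. All of that stands.

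Next, SAP 7.3.1 says the factors were used "to help interpretation of the results rather than any prognostic status". That sentence describes the randomization itself, so it has some bearing on PGI-C, and if it is right R² is near zero and nothing is lost. But it is offered as the reason for an unstratified 2×2 WR test, together with a worry about small strata that does not apply to two main effects in an ANCOVA. Nor did it keep the same factors out of the WIN model.

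The R² values can also be called generous. For one evenly split factor the between-stratum difference is 2√R² residual SDs: 0.45 at 5% and 0.63 at 10%, the latter larger than the assumed drug effect. That stands too; at 2% the marginal gain is only 0.54 points.

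Finally, a reader might infer from 7.2.3 that no PGI-C sensitivity analysis is prespecified. The documents do not support this. Section 4 promises a per-protocol repeat for key secondary endpoints, and Table 7-2 labels both PGI-C scales as such. What is wrong is where the reader is sent. Section 4 names no model for that repeat; if it reuses the ANCOVA, as WIN's repeat reuses its MMRM, it too would lack the factors.

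**Conclusion.** The point holds as a small efficiency and consistency matter. Both PGI-C ANCOVAs omit the randomization factors, and PGI-C is the only confirmatory endpoint pair without a stratum-adjusted result, main or supportive.

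Two stronger readings should be set aside. The tests are not invalid: omitting the factors causes no bias, no inflation of type I error and no change of estimand. Nor is the protocol breached, since its wording is conditional.

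How much power is lost depends on an R² the documents do not give. The loss is nil at zero and a few points at most over the range to 10%, and it counts only if WR and WIN succeed first. The cross-reference error in 7.2.3 is definite whatever R² is, but editorial. Low priority overall.

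**What to change.** Before unblinding, do one of the following for 7.5.2 and 7.5.4:

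- Add Visit 2 Maryland CNC stratum (≥28% against <28%) and laterality as main effects, alongside treatment and baseline PGI-S.
- Keep the present model as confirmatory and prespecify the adjusted model as a sensitivity analysis.

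Either way, write the per-protocol repeat from Section 4 into 7.5.2, 7.5.4 and Table 7-2, or correct the closing sentence of 7.2.3.

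The first option costs two residual degrees of freedom (109 to 107), about 0.01 point of power if the strata are not prognostic. Both factors are already collected for randomization. The administrative cost is one further SAP version. Because version 2.0 already revised the primary analysis and the testing sequence after randomization was complete, the sponsor may prefer the second option, which leaves the confirmatory models untouched and still supplies the missing stratum-adjusted result, but recovers no power in the confirmatory tests.
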